6.4. Interim Analyses and Data Monitoring⁵

No interim analysis is planned in the study.

6.5. Multi-center Studies

Data from all centers will be merged and analyzed as one population for all study endpoints.

6.6. Multiple Testing

No adjustment for multiplicity is planned.

7. Summary of Study Data

Demographic and other baseline characteristics, efficacy and safety data will be summarized by time point of assessment and listed.

Default Summary Statistics

The default summary statistics for quantitative and ordinal variables will be the number of observations (n), mean, standard deviation (SD), median, minimum (Min) and maximum (Max).

Default Frequency Tabulations

For qualitative variables, the number and percentage (n, %) of patients with non-missing data per category and total number of patients with non-missing data where applicable (n') will be the default summary presentation.

For AEs and medical history, however, the denominator for the percentage calculation will be the number of patients at risk. A patient will be considered at risk if the patient is in the Treated set.

⁵ This section is based on the section 6.6 “Interim analysis” of clinical study Protocol.

ML39355_STATISTICAL ANALYSIS PLAN_Final 2.0_17 June 2020

The number of decimals for each descriptive statistic will be determined by the following rules:

- mean, median: +1 decimal symbols compared to the analysed variable values;
- standard deviation: +2 decimal symbols compared to the analysed variable values;
- minimum and maximum values: the same as for the analysed variable values;
- percentages will be rounded to one decimal symbol;
- confidence intervals will be presented with accuracy of the estimated value.

The maximum number of decimal places in the statistical report is four. If some descriptive statistic has more than four decimal places after above mentioned rules application, this value will be rounded to four decimal places.

Statistical Tests and Common Calculations

Unless otherwise specified in the description of the analyses, the following arrangements will be applied:

- 95% two-sided confidence intervals (CI);
- [if appropriate] CIs for mean values will be calculated based on normal distribution (SAS procedure UNIVARIATE with CIBASIC option);
- [if appropriate] CIs for proportions will be computed using the exact (Clopper-Pearson) method.
- Type I error values (p-values) will be rounded to four decimal symbols.

For descriptive statistics and analysis, the following rules will be applied:

- “<XX” results (e.g. below the limit of quantification, BLQ) will be replaced by the “XX/2” values;

For quantitative measurements, changes from baseline will be calculated as [value at post-baseline visit X – baseline value].

For change from baseline, the baseline value for a variable in common cases (except for efficacy analysis) is defined as the last non-missing value collected before the first study drug administration.

Study day for each event will be calculated from the reference start date (date when patient was first exposed to study drug).

If the date of the event is on or after the reference date, then

$$study\ day = (date\ of\ event - reference\ date) + 1.$$

If the date of the event is prior to the reference date, then

$$study\ day = (date\ of\ event - reference\ date).$$

For partial dates study day will not be calculated.

The following visit windows will be defined:

ML39355_STATISTICAL ANALYSIS PLAN_Final 2.0_17 June 2020

Visit	First day of the visit window	Last day of the visit window
Week 1 Telephone Assessment (+/- 1 day)	1	8
Week 2 (+/- 2 days)	6	16
Week 4 (+/- 2 days)	20	30
Week 8 (+/- 2 days)	48	58
Week 12 (+/- 2 days)	76	86
Week 16 (+/- 1 week)	99	119
Week 20 (+/- 1 week)	127	147
1st day at Week 26 (+/- 1 week)	169	189
2nd day at Week 26 (+/- 1 week)	169	189
Week 39 (+/- 2 weeks)	253	287
Week 52 (+/- 2 weeks)	344	378

The data from all subjects who were treated in the rollover study will be pulled for the analysis irrespective of the trade name(s) of pirfenidone used by the subject (Esbriet® or other, if applicable). An explanatory footnote will be added to the outputs where necessary to indicate which pharmaceutical product was used.

7.1. Subject Disposition

The following patient disposition summaries will be provided:

- A summary of the number of patients signed the Informed Consent and the number of screen failures with reasons for premature study termination
- A summary of the number of screen failure patients violated any inclusion/exclusion criterion, by criterion
- A summary of the number of patients allocated to treatment, the number and percentage of treated patients, the number and percentage of patients attended each study visit, the number and percentage of patients who were included into rollover study (Allocated to treatment set)
- A summary of the number and percentage of patients included in each population for statistical analysis (Allocated to treatment set)
- A summary of the number and percentage of patients completed the study and prematurely discontinued from the study by major reason for discontinuation (Allocated to treatment set).

By-patient listings of disposition details will be provided for all patients who signed the Informed Consent.

7.2. Protocol Deviations⁶

Number and percentage of patients with at least one protocol deviation will be tabulated (Allocated to treatment set). All protocol deviations will be listed (All Enrolled patients).

⁶ This section is based on the section 9.2 “Protocol deviations” of clinical study Protocol.

ML39355_STATISTICAL ANALYSIS PLAN_Final 2.0_17 June 2020

7.3. Demographic and Baseline Variables ⁷

eCRF form: “DEMOGRAPHIC DATA”, “VITAL SIGNS”.

Descriptive statistics for the following demographic and anthropometric characteristics, which are evaluated at screening, will be presented in accordance with section 7:

- demographic characteristics: age, gender, race, ethnicity;
- anthropometric characteristics: height (cm), weight (kg), body mass index (BMI, kg/m²).

Body mass index will be calculated as *weight (kg) / [height (m)]²*.

eCRF form: “SURGICAL LUNG BIOPSY”, “REVIEW TRANSBRONCHIAL LUNG BIOPSY/BAL”, “HRCT SCAN FOR PATIENT ELIGIBILITY CONFIRMATION”, “DL(CO)”, “SPIROMETRY”, “SEROLOGIC TESTS”, “GAP RISK ASSESSMENT”.

The following parameters will be tabulated in accordance with section 7:

- Disease Assessment and PFT:
 - Surgical lung biopsy (SLB) (if available) (UIP pattern assessment of regional specialist: Consistent, Probable, Possible, Inconsistent / unclassified; UIP pattern assessment of central specialist: Consistent, Probable, Possible, Inconsistent / unclassified)
 - Transbronchial lung biopsy/ Bronchoalveolar lavage (BAL) (if available) (Are there features supporting an alternative diagnosis? Yes/No)
 - High-resolution computed tomography (HRCT) (HRCT fibrosis score; Lung opacity score (Ground-glass opacity))
 - HRCT scan for patient’s eligibility confirmation (UIP pattern assessment of regional CT-specialist: Typical (apparent), Possible; UIP pattern assessment of central CT-specialist: Typical (apparent), Possible, Inconsistent)
 - Carbon monoxide diffusing capacity (DL_{CO} predicted)
 - Pre-, post- bronchodilator, and retrospective FVC (absolute), ml; FVC (relative), % predicted, pre- post-bronchodilator FEV1/FVC,
- Laboratory Tests:
 - Serologic tests: rheumatoid factor, anticyclic citrullinated peptide and antinuclear antibody titer (Positive / Negative)
- PROs and ClinROs:
 - GAP (Gender, Age, Physiology) assessment (Stage, GAP Index (Points), Mortality 1-yr, Mortality 2-yr, Mortality 3-yr)

Specific calculations and/or conversions include but are not limited to the following:

DL_{CO}: Data for DL_{CO} will be collected in the eCRF. Results of DL_{CO} measurements will be corrected to patients’ hemoglobin (Hb) using one of the formulas (Cotes et al. 1979):

$$\text{Hb-corrected DL}_{CO} \text{ for men: } \text{DL}_{CO} \times (10.22 + \text{Hb}) / (1.7 \times \text{Hb})$$

⁷ This section is based on the section 6.3 “Summaries of Demographic and Baseline characteristics”, 4.5.6 “HRCT and Surgical Lung Biopsy”, 4.5.7 “Spirometry and DL_{CO} Measurements”, 4.5.8 “Laboratory, Biomarker, and Other Biological Samples”, 4.5.11.4 “GAP Risk Assessment System” of clinical study Protocol.

**ML39355_STATISTICAL ANALYSIS PLAN_Final 2.0_17 June 2020**

$$\text{Hb-corrected DL}_{\text{CO}} \text{ for women: } \text{DL}_{\text{CO}} \times (9.38 + \text{Hb}) / (1.7 \times \text{Hb})$$

where Hb indicates the value of hemoglobin, in g/dL. If the Hb value is reported in g/L, then the Hb value is divided by 10. If the Hb value is reported in mmol/L, then the Hb value is divided by 0.6206.

Use the hemoglobin value available on the same day if possible; otherwise, the closest hemoglobin value before or after the actual DL_{CO} assessment date should be used. If the two values are equidistant, the value before the actual DL_{CO} assessment should be used.

All data will be listed.

7.4. Concurrent Illnesses and Medical Conditions⁸

eCRF form: “GENERAL MEDICAL HISTORY”, “HISTORY OF IDIOPATHIC PULMONARY FIBROSIS”.

Medical history findings will be coded using the Medical Dictionary for Regulatory Activities (MedDRA) version 22.0 (or further updating) according to Data MATRIX SOP [4], and will be presented by Primary System Organ Class (SOC) and Preferred Term (PT) within SOC.

Medical history events marked as “Resolved” will be considered as prior diseases. Medical history events marked as “Ongoing” will be considered as concomitant diseases.

Prior and concomitant diseases will be tabulated separately.

Medical history findings will be reported on a by-patient basis. This implies that if the patient suffered the same event (mapped to same PT) repeatedly the event will be counted once and only once for appropriate SOC. Within SOC patients may have reported more than one PT. The SOCs and PTs within each SOC will be sorted by descending order of total incidence.

As medical history of main disease, the following parameters: (Idiopathic Pulmonary Fibrosis), Duration of clinical symptoms consistent with IPF (months), Clinically significant environmental exposure known to cause pulmonary fibrosis (Yes/ No), Known explanation for interstitial lung disease (Yes/ No), Cigarette smoking within 28 days before the treatment start (Yes/ No) will be presented descriptively in the separate table.

All data will be listed.

7.5. Prior and Concurrent Medications⁹

eCRF form: “PRIOR/ CONCOMITANT MEDICATIONS”.

⁸ This section is based on the section 4.5.2 “Medical History and Demographic Data”, 6.3 “Summaries of Demographic and Baseline characteristics” of clinical study Protocol.

⁹ This section is based on the section 6.2 “Summaries of conduct of study” of clinical study Protocol.

ML39355_STATISTICAL ANALYSIS PLAN_Final 2.0_17 June 2020

1. Prior and concomitant medications will be analyzed based on the information from the Concomitant/Prior Medications (CM) domain.

2. All prior and concomitant medications will be coded using the World Health Organization Drug Dictionary (WHODD) version B2 March 2018 (or further updating) according to Data MATRIX SOP [4].

Classification of treatment as either Prior or Concomitant will be based on stop date of medication in “PRIOR/CONCOMITANT” eCRF form. The number (%) of patients reporting the use of any medications, and the number of reported medications will be presented in separate tables by pharmacological subgroup (3rd level) and chemical substance (5th level).

Medications that stop prior to the date of first dose of study therapy will be classified as Prior medications. If a medication stops on or after the date of first dose of study therapy (or “ONGOING”) then the medication will be classified as Concomitant. For patients who take part in the rollover study, medications started on or after the date of the first dose of the study drug during the rollover study will be summarized separately.

3. If the information about stop date of medication is missing or incomplete, the rules from section 6.3 will be applied for classification. Medications will be assumed to be concomitant, unless there is clear evidence (through comparison of partial dates) to suggest that the medication stopped prior to the first dose of study therapy. If there is clear evidence to suggest that the medication stopped prior to the first dose of study therapy, the medication will be assumed to be Prior.

By-patient listings will be provided.

8. Efficacy Analyses¹⁰

eCRF form: “SPIROMETRY”.

Descriptive statistics for all efficacy variables will be presented by visit. For the descriptive statistics, the rules presented in section 7 will be applied.

The FAS and Complete case set will be used for the efficacy analysis. Analysis on Complete case set will be one of the sensitivity analyses to be performed.

All efficacy data will be listed.

8.1. Primary Efficacy Analysis

The primary outcome variable is the absolute change in FVC from Baseline to Week 26 (both in mL and % predicted). Baseline FVC will be the average of the FVC measured at the Screening (excluding values after bronchodilator administration) and Day 1 visits, if either is missing, the non-missing value will be used. The FVC at Week 26 will be the average of the FVC measured on

¹⁰ This section is based on the section 6.4 “Efficacy analyses” of clinical study Protocol.

**ML39355_STATISTICAL ANALYSIS PLAN_Final 2.0_17 June 2020**

two separate days at Week 26, if either is missing, the non-missing value will be used. If both values are missing, the data will be imputed as specified in Section 6.3.

Data will be analyzed using standard descriptive statistics for continuous variables and 95% CI for the means and mean changes.

The data imputation methods for primary endpoint are described in Section 6.3.

For the primary analysis, missing data due to death will be replaced with the worst possible value (FVC= 0 mL or 0%). Missing data due to reasons other than death (pattern 3) will be replaced with imputed values based on the average measurements for “similar” patients at that time point (SSD, Primary analysis).

As sensitivity analyses, the following imputation methods will be used:

1. Missing data due to death will be replaced with the worst observed FVC value at week 26. Missing data due to reasons other than death (pattern 3) will be replaced with imputed values based on the average measurements for “similar” patients at that time point (SSD).

2. Missing data due to death will be replaced with an intermediate value (FVC =1500 mL or 50%). Missing data due to reasons other than death (pattern 3) will be replaced with imputed values based on the average measurements for “similar” patients at that time point (SSD).

3. Missing data due to death will be replaced with the worst possible value (FVC= 0 mL or 0%). Missing data due to reasons other than death (pattern 3) will be replaced with LOCF.

4. Missing data due to death will be replaced with the worst observed FVC value at week 26. Missing data due to reasons other than death (pattern 3) will be replaced with LOCF.

5. Missing data due to death will be replaced with an intermediate value (FVC =1500 mL or 50%). Missing data due to reasons other than death (pattern 3) will be replaced with LOCF.

6. Missing data due to death and due to reasons other than death (pattern 3) will be replaced with LOCF.

Analysis of the primary efficacy endpoint will be also repeated on the Complete case set (CCS) without missing data imputation as the sensitivity analysis. Complete case set will include patients related to pattern 1 and 2 (section 6.3), results will be reported for pattern 1 and 2 separately and overall.

Primary analysis with missing data imputation of the primary efficacy endpoint and analysis on the CCS set will also be repeated excluding all values outside of visit window based on visit window definitions in Section 7.

For this analysis, if one of the observations pertaining to Week 26 visit is within the visit window and the other is outside the visit window, the observation which is within the visit window will be used for Week 26 assessment. The distribution (number and percentage) of primary outcome variable across three categories of change from Baseline (Decline of $\geq 10\%$ or death

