4.1.1 Inclusion Criteria

Patients must meet the following criteria for study entry:

1. Male and female patients aged 40–80 years, inclusive.
2. Clinical symptoms consistent with IPF of ≥ 6 months duration.
3. Patients should have both “confident” or “consistent” with UIP diagnosis of IPF based on clinical, radiologic or pathologic data according to 2011 ATS/ERS guidelines at the Screening. HRCT scan performed within 24 months before the start of the Screening may be used.
4. No features supporting an alternative diagnosis on transbronchial biopsy, bronchoalveolar lavage (BAL), or surgical lung biopsy, if performed. Results of the surgical lung biopsy performed within the last 4 years must be confirmed by central review.
5. Patients with %FVC ≥ 40 % at the Screening.
6. Patients with %DL_{CO} ≥ 30 % at the Screening.
7. Ability to walk ≥ 100 m during the 6-minute walk test at the Screening.
8. Eligible patients must discontinue all prohibited medications at least 28 days before the *start of treatment*.
9. Female patients of childbearing potential must have negative urine pregnancy test at the Screening and before first dosing on Day 1.

Pirfenidone—F. Hoffmann-La Roche Ltd

10. Patients able to conceive must agree to use safe contraceptive methods for the whole duration of the study and 28 days after the last dosing.

- a. For women of childbearing potential: agreement to remain abstinent (refrain from heterosexual intercourse) or use a highly effective contraceptive method with a failure rate of < 1% per year during the treatment period and for at least 28 days after the last dose of pirfenidone. A woman is considered to be of childbearing potential if she is postmenarcheal, has not reached a postmenopausal state (≥ 12 continuous months of amenorrhea with no identified cause other than menopause), and has not undergone surgical sterilization (removal of ovaries and/or uterus). Examples of highly effective contraceptive methods with a failure rate of < 1% per year include bilateral tubal ligation, male sterilization, hormonal contraceptives that inhibit ovulation, hormone-releasing intrauterine devices (IUD), and copper intrauterine devices.
- b. For men: agreement to remain abstinent (refrain from heterosexual intercourse) or use contraceptive measures, and agreement to refrain from donating sperm, as defined below:

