**ML39355_STATISTICAL ANALYSIS PLAN_Final 2.0_17 June 2020**

permanent use of corticosteroids (prednisolone at a maximum daily dose of 15 mg or equivalents) and brief periods of corticosteroid use for acute IPF exacerbation, patients will not receive any other therapy for the treatment of IPF. After central review of HRCT and SLB, patients will enter the Screening period, which may last up to 28 days (4 weeks).

After the Screening, eligible patients will enter the Treatment period lasting 26 (\pm 1) weeks. All patients will receive pirfenidone 2403 mg/d administered orally in divided doses three times per day (TID) with food. Dose of the study treatment will be titrated over 14 days to the full dose of 9 capsules per day (three 267 mg capsules taken orally TID with food). Patients will remain on a stable maintenance dose for the duration of the treatment period unless the dose is reduced to manage adverse events or titrated again when restarting study treatment after an appropriate interruption in treatment.

The primary efficacy endpoint in the study is the change from baseline to Week 26 in absolute (mL) FVC and relative (%) FVC as measured by spirometry procedure. Spirometry will be performed at the Screening, on Day 1 of treatment, at Week 12, Week 26 and in the extended Follow-up period (Weeks 39 and 52), if applicable. At screening, spirometry measurements will be performed before and after administration of albuterol (or salbutamol) from a metered dose inhaler. During further visits, bronchodilator test is not necessary to perform. Spirometry data collected throughout the study will be evaluated by local readers.

Patients will have a telephone assessment at Week 1, when safety-related information and adherence to treatment is collected. Subsequently patients will have in-clinic visits at Weeks 2, 4, 8, 12, 16, 20 and 26. Patients should complete an adverse event and dosing compliance diary between all visits. Additionally, telephone calls to patients will be scheduled at Weeks 3, 5, 7, 13 and 24 as a part of IPF care program. A total of 5-7 calls are scheduled in the study, including extra-calls at Weeks 8 and 10 as needed.

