6.3. Missing Data⁴

For missing FVC data imputation, patients will be classified into different patterns depending on the availability of data:

Patients with a 26 week FVC value:

1. those who received study drug until 26 weeks (completed the treatment period);
2. those who prematurely discontinued study drug, but who were followed up until Week 26.

Patients without a 26 Week FVC value:

3. those who were alive at 26 weeks;
4. those who died before 26 weeks.

Missing data at other visits before Week 26 (primary outcome variable) will not be imputed.

The following imputation methods including sensitivity analyses will be applied for patients with pattern 3 - 4:

Assuming that deaths of the patients (pattern 4) is likely to be related to worsening of IPF, these unobserved FVC values should be lower than those in patients who did not die prior to Week 26.

Methods for handling missing data due to death will include the following:

- Replacement with the worst possible value (FVC= 0 mL or 0%) (Primary analysis).
- Replacement with worst observed averaged FVC value at week 26 (Sensitivity analysis).

⁴ This section is based on the section 6.2 “Summaries of conduct of study” of clinical study Protocol.

ML39355_STATISTICAL ANALYSIS PLAN_Final 2.0_17 June 2020

- Replacement with an intermediate value (FVC =1500 mL or 50%) (Sensitivity analysis).

Missing data due to reasons other than death (e.g., missing visits, early withdrawal from the study, including missing values due to lung transplantations) (pattern 3) will be replaced with imputed values based on the average measurements for “similar” patients at that time point. Similar patients are those without missing data before that time point and whose data have the smallest sum of squared deviations (SSD) from that patient for all visits prior to the one with the missing data. Missing data due to lung transplant will be imputed using the SSD method even if the patient dies after lung transplant.

The procedure referred to as the sum of squared deviations (SSD) is outlined as follows:

Step 1: For post-Baseline missing value to be imputed at a visit (Visit week 26) for a particular patient (Patient A), a set of all patients without any missing values for visits from Baseline up to Visit week 26 as Patient A will be selected.

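### In sensitivity analyses 2 and 5, a death in a patient whose baseline FVC is below the imputed constant (50% or 1500 mL) counts as a gain in mean change

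*SAP*

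**What the plan says.** SAP 8.1 lists six imputation-based sensitivity analyses. Analyses 2 and 5 treat deaths alike: "Missing data due to death will be replaced with an intermediate value (FVC =1500 mL or 50" (% predicted). They differ only in how other missing values are filled (sum of squared deviations, SSD, in analysis 2; LOCF in analysis 5). The same constant stands in SAP 6.3, Protocol 6.2 and the protocol synopsis. None of these places caps it at the patient's own values.

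Three other statements determine what the constant does:

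- SAP section 7, on the sign of a change: "changes from baseline will be calculated as [value at post-baseline visit X – baseline value".
- Protocol 4.1.1, on entry: "Patients with %FVC ≥ 40 % at the Screening". There is no FVC criterion in mL.
- SAP 6.3, on the reason for imputing deaths separately: "deaths of the patients (pattern 4) is likely to be related to worsening of IPF, these unobserved FVC values should be lower" than in patients alive at Week 26.

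Table 2.2 reports the mean change for each of analyses 1 to 6. Table 2.3 puts every death in the worst of three categories, whatever value is imputed.

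**The concern.** An intermediate value for a death should lie between the worst possible value and no harm. A fixed 50% or 1500 mL does so only for patients who start above it. Below it, death is scored as better than staying stable. A patient who dies after a baseline of 42% is given 50%, while a survivor who stays at 42% keeps 42%. Table 2.2 would count that death as an improvement and Table 2.3 would count it in the worst category.

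These analyses exist to show how the mean change depends on the value given to deaths. For low-baseline patients the dependence has the wrong sign. The two scales can also disagree within one patient, because 1500 mL equals 50% only when predicted FVC is 3000 mL.

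**Working it through.** **The plan's own figures.** The documents give no numerical result for analyses 2 and 5. The relevant yardstick is the planned precision in SAP section 5: 1.96 × 20 / √60 = 5.06 points, which reproduces the stated margin of about 5.

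**Inputs.** Constant 50% or 1500 mL (SAP 8.1); death value 0 in the primary analysis (SAP 8.1); entry from 40% (Protocol 4.1.1); n = 60, baseline mean 67.8 and SD 11.24 from the cited phase III trial, falling to 65.3 at Week 26, a change of -2.5 (SAP section 5).

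**Per patient** (change = imputed value - baseline):

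| Baseline | Analyses 2 and 5 | Primary analysis |
|---|---|---|
| 42% | 50 - 42 = +8 | 0 - 42 = -42 |
| 46.4% | 50 - 46.4 = +3.6 | -46.4 |
| 55% | 50 - 55 = -5 | -55 |
| 1300 mL | 1500 - 1300 = +200 mL | -1300 mL |

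The sign needs no assumption. For disagreement between scales, assume a predicted FVC of 4000 mL. A baseline of 45% is then 0.45 × 4000 = 1800 mL, and the death scores +5 points but 1500 - 1800 = -300 mL.

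**How many patients start at 40-50%.** This assumes a normal distribution truncated at 40. With mean 67.8 and SD 11.24 the share is 5.0%, or 3.0 of 60, with a mean of 46.4% in that band. Broader assumed distributions, as mean (SD), give 8.9% for 67.8 (15), 11.6% for 65 (15) and 14.6% for 62 (14), so about 5 to 9 of 60.

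**Study mean** (assumed: all other patients at -2.5, last observed FVC equal to baseline). The capped rule is the one proposed under the fix.

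- One death at 46.4%: current (59 × -2.5 + 3.6)/60 = -2.398; capped (59 × -2.5 + 0)/60 = -2.458; difference 0.060.
- The same with a last value 3 points below baseline: capped (59 × -2.5 - 3)/60 = -2.508; difference 0.110.
- One death at 42%: current -2.325; capped -2.458; difference 0.133; primary -3.158.
- Three deaths at 42%: current (57 × -2.5 + 24)/60 = -1.975; capped (57 × -2.5)/60 = -2.375; difference 0.400; primary (57 × -2.5 - 126)/60 = -4.475.

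**mL scale** (same baseline distribution, predicted FVC assumed). At 3000 mL the mean baseline below 1500 mL is 1392, so one death shifts the mean by 108/60 = 1.8 mL. At 2500 mL it is 1346, giving 154/60 = 2.6 mL. At 4000 mL the lowest qualifying value is 1600 mL, so there is no shift.

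**How many such deaths.** The first scheduled post-baseline FVC, walk test and EQ-5D are at Week 12, and the FAS needs one post-baseline efficacy value. The exposed window is therefore taken as Weeks 12-26. With the 1-year mortality by GAP stage in Protocol Appendix 6, a constant hazard (assumed) and three low-baseline patients:

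- Stage I: 3 × (1 - 0.944^(14/52)) = 0.05
- Stage II: 3 × (1 - 0.838^(14/52)) = 0.14
- Stage III: 3 × (1 - 0.608^(14/52)) = 0.38

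**The case against.** The strongest objection is that this hardly matters. One typical death shifts the mean by 0.06 to 0.11 points. Multiplied by 0.14 to 0.38 expected deaths, the expected shift is about 0.01 to 0.04 points, under 1% of the half-width. Stage I is reachable with FVC below 50%, and the protocol excludes patients judged to have less than 12 months to live, so the true number of deaths may be lower still. Table 2.2 already shows the 0% rule, the worst observed value, LOCF and complete cases beside these results. All of that stands, and it keeps the point minor. In the other direction, three deaths at 42% is near the worst case only if 5% of patients start below 50%; the broader distributions leave room for more.

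A second objection is that SAP 6.3 compares FVC levels between deaths and survivors, not one patient's change, and that 50% is below the cited Week 26 mean of 65.3. That is fair at group level. It does not answer the sign, because Table 2.2 reports change and each low-baseline death enters it as a gain.

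A third is that other analyses can also credit a death: 1 and 4 ("Missing data due to death will be replaced with the worst observed FVC value at week 26") and 6 ("Missing data due to death and due to reasons other than death (pattern 3) will be replaced with LOCF"). They can, but only if the imputed value happens to exceed that patient's baseline. In analyses 2 and 5 it is certain for every baseline below the constant.

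**Conclusion.** The concern holds and is minor. On the matching scale, every imputed FAS death with a baseline below 50% or 1500 mL enters the mean change of analyses 2 and 5 as a gain. This follows from the plan's own definitions. Its size rests on assumptions about baseline spread, number of deaths and change in the other patients: about 0.06 points for one typical death and 0.40 for three at 42%, against a half-width of about 5.

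The primary analysis, analysis 3 and Table 2.3 are unaffected. Deaths without any post-baseline efficacy value are outside the FAS. For transplant, SAP 6.3 applies a different rule: "Missing data due to lung transplant will be imputed using the SSD method even if the patient dies after lung transplant". No decision depends on analyses 2 and 5.

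**What to change.** In analyses 2 and 5, impute for a death the smallest of the patient's baseline FVC, last observed FVC and the constant (50% or 1500 mL). With no post-baseline FVC, use the smaller of baseline and the constant. A death then cannot count as an improvement in these two analyses. For a baseline of 42%:

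- Week 12 at 45%: min(42, 45, 50) - 42 = 0
- Week 12 at 52%: min(42, 52, 50) - 42 = 0
- Week 12 at 39%: min(42, 39, 50) - 42 = -3

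The cost is one line of programming in two sensitivity analyses. SAP 6.3 and 8.1 need the new wording. Because Protocol 6.2 and the synopsis carry the uncapped constant, the departure must be recorded in SAP section 14, which now states full consistency with the protocol.

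The fix has limits. A death can still be scored as no change, which is better than the assumed average of -2.5. For low-baseline deaths the rule comes close to LOCF capped at baseline, so it overlaps with analysis 6. It also lowers the value for deaths whose baseline is above the constant but whose last FVC is below it. Analyses 1, 4 and 6 are left as they are.
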